# 7.5 Sample Size Determination

If the true  $\pi$  is equal to 0.90, then, a 1-sided exact binomial test at alpha=0.05 with 216 eyes (108 subjects) has 99% power.

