# Statistical Considerations

The objective of the statistical analysis is to evaluate agreement in sphere, cylinder, and axis measurements between LFR-260 and traditional refraction performed by a traditional phoropter. Specifically, the subjective manifest refraction measured by means of a traditional phoropter will serve as the reference control and is considered to be the gold standard for the purpose of this evaluation.

The accuracy of the acuity measurement obtained by the LFR-260 will be evaluated for both cases (uncorrected, corrected) measured with the conventional phoropter. It will be assessed comparing the LFR-260 acuity measurement to the conventional acuity measurement using a Snellen chart (scored to the letter), with similar analyses used for the refractive components.

For each measurement, the paired difference will be computed. Good clinical agreement is defined a priori as  $\leq \pm 0.5$  D for sphere and cylinder measurements and  $\leq \pm 10$  degrees for axis measurements for subjects with low astigmatism and  $\leq \pm 5$  degrees for axis measurements for subjects with low astigmatism.

The unit of analysis will be the individual eye. Overall device performance will be summarized as the number of and percentage of eyes meeting three of the good clinical agreement criteria listed above.

the mean of measurements will characterized.

A supporting analysis will evaluate the vector difference between investigational device measurements and the gold standard in terms of sphere and cylinder measurements. The vector differences is square root of (X1-Y1) + (X2-Y2) where the X1 and X2 are measurements of sphere and cylinder using the investigational devices and Y1 and Y2 are the same measurements using the gold standard.

Homogeneity of treatment effects across sites will be evaluated comparing site level differences between the investigational device and the gold standard separately for sphere, cylinder, and axis and also for the vector analysis of sphere and cylinder.

Similarly, differences between measurements from the investigational device and the gold standard device will be summarized by gender, age category, race, and ethnicity to investigate consistency or heterogeneity of the treatment effect across those subgroups, separately for sphere, cylinder, and axis and also for the vector analysis of sphere and cylinder.

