# 3.2 Number of Subjects

Accounting for lost to follow-up, a total of up to 108 subjects (216 eyes) will be enrolled in the study. To control any effect of the instrument induced myopia, we expect to enroll an age tiered distribution of participants of the following approximate percentages:

- Approximately 45% Pediatrics (age from 12 until ≤21 years)
- Approximately 55% Adults/Geriatrics (age between 22-65)

A large portion of the subjects belongs to pediatric population such distribution will address the presence or absence of induced instrument myopia.

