# 4.4 Visual Acuity Testing Procedure

All the subjects will undergo the standard visual acuity testing using both the LFR-260 and the traditional phoropter. Both eyes will be tested, always starting with the right eye. Both eyes will be tested with a traditional phoropter and the LFR-260. The subject will be seated on a height adjustable chair to ensure comfort during the test. Once the subject is seating comfortably the examiner will measure the distance between the outer canthus of the eye and the visual acuity to be used. The left eye will be patched while testing the right eye and vice versa. They could be covered with the occlude or using the masking capabilities of the LFR-260.

The following outcomes will be measured (for both eyes):

- Unaided VA
- Aided VA
- Distance for the test

Evaluation of the refractive state should be performed by reading the Snellen chart (or equivalent depending on the patient) at 20 feet (or adjusted to the appropriate distance depending on the dimensions of the actual optometric office). The subject should be informed that the chart only includes letters (or equivalent for patient population).

Outcomes will be recorded. If a line was incomplete, the scored letters should be added to the VA. The goal is to obtain best corrected visual acuity (20/20 Snellen) to ensure that the highest level of visual acuity possible for the patient.

Visual acuity testing will be performed without the use of cycloplegic agents and or pupil dilation at all times. To control the potential effect of instrument myopia we will propose starting the examination using the fogging method to relax any potential accommodation.

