# 7.4 Primary Effectiveness Hypothesis

The primary hypothesis for this study is that the probability of simultaneously achieving good clinical agreement for sphere, cylinder, and axis exceeds a performance goal for measurements made by the LFR-260 compared to those obtained using the control device, *traditional phoropter*.

Symbolically, the null and alternative effectiveness hypotheses are: :

Ho:  $\pi \le PG$ Ha:  $\pi > PG$ 

Where  $\pi$  is the true probability that the LFR 260 is within 0.5D (+/-) in measuring sphere and cylinder results and within 10 degrees for axis results among subjects with low astigmatism and within 5 degrees among subjects with moderate to high astigmatism from the traditional phoropter.

For this study, PG is set to 0.80.

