# 7.6 Testing of Primary Effectiveness Hypothesis

The lower bound (LB) of a 1-sided exact binomial confidence interval will be determined and compared to 0.80. If LB exceeds 0.80, the device will have met the a priori defined performance goal.

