# 7.7.3 Poolability and Homogeneity of Treatment Effects

The primary analysis will be based on the ITT analysis set and will use multiple imputation to address missing values. The MI model will include sphere, cylinder, and axis measurements for both the investigational device and the gold standard device and baseline characteristics including age and gender. Analyses will be repeated in a per protocol analysis set that includes eyes will complete data. A tipping point analysis will be performed to evaluate the robustness of results with regard to the missing-at-random (MAR) assumption necessary for the validity of the MI analyses.

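### The primary exact binomial bound treats 216 eyes from 108 subjects as independent; its one-sided type I error exceeds 5% once the between-eye correlation is above about 0.05

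*Combined protocol and SAP*

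**What the plan says.** - Unit of analysis (synopsis, Statistical Considerations): "The unit of analysis will be the individual eye".
- Testing (Section 4.4): "Both eyes will be tested with a traditional phoropter and the LFR-260". Every subject therefore contributes two results.
- Enrolment (Section 3.2): "a total of up to 108 subjects (216 eyes) will be enrolled in the study".
- Goal (Section 7.4): "For this study, PG is set to 0.80".
- Power (Section 7.5), at a true rate of 0.90: "a 1-sided exact binomial test at alpha=0.05 with 216 eyes (108 subjects) has 99% power".
- Decision rule (Section 7.6): "The lower bound (LB) of a 1-sided exact binomial confidence interval will be determined and compared to 0.80". The goal is met if the bound is above 0.80.
- Missing data (Section 7.7.3): "The primary analysis will be based on the ITT analysis set and will use multiple imputation to address missing values".

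No section gives a between-eye correlation, a design effect, a clustered or subject-level interval, a GEE or mixed model, or a subject-level sensitivity analysis. The imputation text does not mention the pairing either. Section 7.3 words the endpoint as a proportion of subjects, which does not match the eye-level test.

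**The concern.** An ordinary exact binomial bound takes its error rate from independent results, and this design yields 108 pairs. Fellow eyes share several features that the protocol itself describes. Instrument myopia is a named concern (Sections 3.2 and 4.4). Anisometropia is capped at 1.5 D (Section 3.4). Device order is randomized per subject, and both eyes are tested at the same visit. A positive correlation of the pass/fail result is therefore plausible, although the documents do not measure it.

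With positive correlation, the number of passing eyes varies more than the binomial allows and the planned lower bound sits too high. The error favours the device, and this one bound decides the only hypothesis test in the study.

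**Working it through.** **Inputs.** 216 eyes from 108 subjects and one-sided alpha 0.05 (Section 7.5); goal 0.80 (Section 7.4); assumed true rate 0.90 (Section 7.5). The between-eye correlation ρ of the pass/fail result is not in the documents and is varied from 0 to 1.

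**Step 1: the plan's own figure.** Let X be the number of passing eyes. For X ~ Bin(216, 0.80), P(X ≥ 182) = 6.64% and P(X ≥ 183) = 4.61%. The exact one-sided 95% lower bound is 0.7960 at 182 and 0.8011 at 183, so the rule is at least 183 of 216 (84.7%). At 0.90, P(X ≥ 183) = 99.46%, which agrees with the stated 99%.

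**Step 2: the same rule with paired eyes.** With rate p and correlation ρ, one subject has

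- P(both pass) = p² + ρp(1−p)
- P(one passes) = 2p(1−p)(1−ρ)
- P(neither passes) = (1−p)² + ρp(1−p)

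At p = 0.80 these are 0.64 + 0.16ρ, 0.32(1−ρ) and 0.04 + 0.16ρ. The mean of X stays at 172.8. Its variance is 216 × 0.16 × (1+ρ) = 34.56(1+ρ), so its SD rises from 5.88 at ρ = 0 to 7.20 at ρ = 0.5. Convolving 108 such pairs gives the exact distribution of X.

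**Step 3: the replacement bound.** Let Yᵢ be the number of passing eyes in subject i. An intercept-only logistic GEE with subject as cluster gives

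logit LB = logit(p̂) − 1.645√V, with V = Σ(Yᵢ − 2p̂)² / [216 p̂(1−p̂)]².

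Its size and power come from full enumeration of the counts of subjects with neither, one or both eyes passing, with complete data.

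| ρ (assumed) | Planned rule: type I error | Planned rule: power at 0.90 | GEE bound: type I error | GEE bound: power at 0.90 |
|---|---|---|---|---|
| 0 | 4.6% | 99.5% | 4.7% | 99.4% |
| 0.05 | 5.0% | 99.3% | – | – |
| 0.1 | 5.4% | 99.2% | 4.7% | 98.8% |
| 0.2 | 6.2% | 99.0% | – | – |
| 0.3 | 7.0% | 98.7% | 4.7% | 97.3% |
| 0.5 | 8.6% | 98.1% | 4.7% | 95.2% |
| 0.7 | 10.0% | 97.5% | 4.5% | 92.9% |
| 1 | 10.7% | 96.0% | 3.9% | 88.0% |

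The planned rule crosses 5% at ρ = 0.048 and peaks at 11.6% near ρ = 0.96. A simulation with 1,000,000 replicates gave 8.61% at ρ = 0.5, against 8.57% exactly.

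**Step 4: a result on which the verdict turns.** Take 183 of 216 eyes passing: 84 subjects with both, 15 with one, 9 with neither.

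- p̂ = 183/216 = 0.8472 and logit(p̂) = ln(183/33) = 1.713.
- Estimated ρ = 1 − (15/108)/(2 × 0.8472 × 0.1528) = 0.46.
- Sum of squares = 84 × 0.3056² + 15 × 0.6944² + 9 × 1.6944² = 40.92.
- V = 40.92/27.96² = 0.0523, so √V = 0.2288.
- Logit LB = 1.713 − 1.645 × 0.2288 = 1.337, which back-transforms to 0.792.

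The planned bound for the same data is 0.801. The plan passes the device and the clustered bound fails it.

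**The case against.** The strongest points on the other side are these.

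- **The 0.05 crossing belongs to exactly 216 eyes.** Enrolment is up to 108 subjects and the exact test is discrete. For 90 to 107 subjects the crossing ranges from about 0.006 (99 subjects) to 0.24 (96 subjects). At ρ = 0.05 itself the error is 5.01%, which is of no practical weight. This stands as a limit on the threshold. It does not remove the problem: at ρ = 0.5 the error is still 6.8% to 9.0% for the sizes tried between 96 and 107 subjects.
- **The relevant correlation is unknown.** It is that of a composite pass/fail on between-device differences, not of raw refraction. The bound also holds 5% at zero, slightly negative or very small positive correlation (4.2% at −0.05). This stands: the defect in the method is certain, but its size is conditional. The 11.6% maximum needs a correlation near 0.96 and should carry little weight.
- **Power is barely affected.** True for the planned rule, which keeps 98.1% at ρ = 0.5. The lower figures belong to the replacement bound.
- **GEE is one option, and it is asymptotic.** A subject-level exact analysis, a design-effect interval or a cluster bootstrap would also address the pairing. The GEE figures assume 108 complete pairs and a common rate, and have not been shown under imputation. Clustering by the six examiners at three locations (Section 3.1) remains outside it. These points limit what the remedy can claim, but none makes the planned bound valid for paired eyes.

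**Conclusion.** The concern holds and should be fixed before analysis. Sections 7.5 and 7.6 apply an independent-eye method to paired eyes, and nothing in the documents corrects for it. For 108 complete pairs with a common agreement rate and no examiner effect, the nominal 5% error becomes 7.0% to 10.0% at assumed correlations of 0.3 to 0.7, and is close to 5% only if the correlation is near zero. The 99% power is arithmetically right for independent eyes, and 108 subjects remain enough.

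**What to change.** **Section 7.6**, as the single primary bound:

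> *The probability of agreement will be estimated by an intercept-only logistic GEE with the eye as observation, subject as cluster and robust variance. The logit estimate and its variance will be combined over imputations by Rubin's rules. The goal is met if the one-sided 95% lower bound, back-transformed to a proportion, exceeds 0.80.*

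The text should also name the reference distribution for the pooled bound (normal or t) and a fallback if every eye passes in an imputed dataset, where the logit is undefined. That case is remote: even with fully concordant eyes at 0.90 its probability is 0.9^108, about 0.00001. The logit scale also closes a separate gap, since Section 7.7.3 makes multiple imputation primary and an exact bound on one count cannot be pooled directly over imputations.

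**Section 7.5**, restated and labelled as an assumption:

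> *With 108 subjects and complete data, if the true rate is 0.90, power is about 93% to 97% for an assumed between-eye correlation of 0.7 down to 0.3, and 88% if fellow eyes always agree.*

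The statement must stay tied to 108 subjects; with 90 subjects and fully concordant eyes, power is 81%.

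**Cost.** SAP wording and a few lines of code, with no extra subjects. The stated power is less favourable and there is no longer one fixed pass mark. It is 183 eyes if the estimated correlation is about 0.03 or less, 184 up to about 0.27, 185 up to about 0.51, 186 up to about 0.77, and 187 to 188 above that.

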# 7.6 Testing of Primary Effectiveness Hypothesis

The lower bound (LB) of a 1-sided exact binomial confidence interval will be determined and compared to 0.80. If LB exceeds 0.80, the device will have met the a priori defined performance goal.

# 7.7 Other Planned Analyses

#### 7.7.1 Bland-Altman Agreement Analysis

Supporting analyses will evaluate the distribution of paired differences between LFR-260 and reference for the three dimensions (sphere, cylinder, and axis) using Bland-Altman agreement analysis. This will include determination of the standard deviation of paired differences, the 95% limits of agreement, and an evaluation of systematic bias. The Bland-Altman plot of paired differences versus the mean of measurements will be provided. The relationship between bias and the mean of measurements will characterized. The same analysis will be applied to the vector difference between LFR-260 measurements and the gold standard in terms of sphere and cylinder measurements. The vector differences is square root of (X1-Y1) + (X2-Y2) where the X1 and X2 are measurements of sphere and cylinder using the investigational devices and Y1 and Y2 are the same measurements using the gold standard.

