# 1.2 Device Name and Intended Use

The LFR-260 is intended to be used for distance vision testing in any environment, may it be in optometric clinics or in the field outside of the clinic, because of its compact form factor and portability.

The LFR-260 is an application-controlled instrument providing capabilities for distance vision testing including sphere, cylinder, and axis. The visual acuity and eye subjective manifest refraction determination will always be administered by an eye care professional (ECP) licensed and registered by the appropriated body in the region intended to be used. The instrument is designed in a way that it will only work with approved personnel and the use of secure credentials.

The device is intended to be used in patients aged from 12-65 years old with healthy visual systems and a refractive error no bigger than (+10 to -15D) and astigmatism no bigger than 2.5D (if any).

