#### 3.4 Inclusion criteria

Participants must fulfill all of the following criteria in order to be eligible for the study:

- 1. The participant or legal guardian is willing and able to understand, sign and date the Ethics committee approved study specific Informed Consent Form.
- 2. The participant is a male or female between the ages of 12 and 65 (inclusive).
- 3. The participant has a history of the following:
  - O No more than mild to moderate far-sightedness or near-sightedness (i.e. Spherical equivalent refraction (SER) between +10 to -15).
  - o an astigmatism of 2.5D or less.
  - o an anisometropia of 1.5D or less.
- 4. The participant is free of ocular and systemic abnormalities that might affect visual functions.

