# 4.3 Control group

The control group is a traditional refraction performed by a phoropter. The results for both refractions will be recorded separating the components Sphere (S), Cylinder (C) and Axis (A). A calculation of the spherical equivalent will be performed at the end of the visit and both values will be recorded in the study documentation. The best corrected visual acuity for each measurement will be recorded.

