#### 7.2.3 Per Protocol

Primary effectiveness analyses may be repeated in a Per Protocol (PP) analysis set. The PP analysis set will exclude from the ITT analysis set patients that had clinically significant violations of inclusion or exclusion criteria or post randomization protocol violations that may reasonably be predicted to impact on effectiveness endpoints and those that have missing data.

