# 7.3 Primary Effectiveness Endpoint

The primary effectiveness endpoint is to demonstrate that the LFR-260 is within 0.5D (+/-) in measuring sphere and cylinder results and within 10 degrees for axis results among subjects with low astigmatism and within 5 degrees among subjects with moderate to high astigmatism from the traditional phoropter in a very large proportion of subjects.

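### Axis is given linear summaries with no 180-degree wrap rule, and the three-part primary endpoint has no scoring rule for eligible zero-cylinder eyes, which have no axis

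*Combined protocol and SAP*

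**What the plan says.** **Axis analyses.** Section 7.7.1: "Supporting analyses will evaluate the distribution of paired differences between LFR-260 and reference for the three dimensions (sphere, cylinder, and axis". The section then asks for the SD of the differences, 95% limits of agreement and a plot of difference against mean. Section 7.7.2 compares axis differences across sites and subgroups. Section 7.7.3 enters axis from both devices in the multiple imputation (MI) model behind the primary intent-to-treat analysis. Section 7.7.4 lists axis among the continuous variables for the ICC. No section mentions wrapping at 180 degrees, a circular mean or a conversion to power-vector components. The plan's vector analysis uses sphere and cylinder only, so it does not fill the gap.

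**Primary endpoint.** Section 7.4 tests whether "the probability of simultaneously achieving good clinical agreement for sphere, cylinder, and axis exceeds a performance goal" of 0.80. The axis limits are "within 10 degrees for axis results among subjects with low astigmatism and within 5 degrees among subjects with moderate to high astigmatism" (Section 7.3). The synopsis (Statistical Considerations) takes the eye as the unit of analysis and reports the "percentage of eyes meeting three of the good clinical agreement criteria listed above". Section 4.3: "The results for both refractions will be recorded separating the components Sphere (S), Cylinder (C) and Axis (A").

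**Eligibility.** Section 3.4 admits "an astigmatism of 2.5D or less", with no lower limit. Section 1.2 describes the intended population as having "astigmatism no bigger than 2.5D (if any"). Eyes without astigmatism are therefore in the study population, and no section says how their axis component is scored.

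**Per-protocol set.** Section 7.2.3 removes patients with violations "predicted to impact on effectiveness endpoints and those that have missing data". The synopsis and Section 7.7.3 describe the same set by eyes with complete data.

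**The concern.** An axis of 1 degree and one of 179 degrees are 2 degrees apart. Ordinary subtraction calls them 178 apart and places their mean at 90. Bland-Altman limits and ICCs depend on squared differences, so a handful of such eyes can dominate them and make a well-agreeing device look poor on axis. The same problem enters the MI model if raw axis is used.

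The second gap bears on the primary result. An eye with zero cylinder on both devices can meet the sphere and cylinder criteria but has no axis to compare. Read literally, the requirement for simultaneous agreement and the synopsis count of three criteria make it a failure. Yet axis limits are set only for low and for moderate-to-high astigmatism, so one can equally argue that no axis criterion applies. If the blank axis is treated as missing, the MI model would supply a value that does not exist. Zero cylinder on one device only is not covered either. In an open-label study, a scoring choice with this much leverage should not be left until the data are visible.

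**Working it through.** **1. The plan's own figure.** Inputs (Sections 7.4 to 7.6): 216 eyes, performance goal 0.80, true agreement 0.90, one-sided exact test at 0.05, eyes treated as independent. The smallest passing count is 183: P(X ≥ 183 | 216, 0.80) = 0.046, and the exact lower bound is 0.801 at 183 and 0.796 at 182. Power is P(X ≥ 183 | 216, 0.90) = 0.995, so the stated 99% reproduces.

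**2. Wrap-around.** For readings of 178 and 4, the raw difference is 174 and the raw mean is 91. The wrapped difference is min(174, 180 − 174) = 6 and the mid-axis is 1.

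Assumptions, as the documents give neither: axes uniform over 0 to 180, and true difference d normal with mean 0 and SD 2 or 3. An eye wraps with probability |d|/180.

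- Wrapped share w = E|d|/180, with E|d| = SD × √(2/π)
- Raw variance = 180·E|d| − E(d²)
- ICC = 1 − raw variance/5400, since a uniform axis has variance 180²/12 = 2700

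| Assumed SD | E\|d\| | w | Raw variance | Raw SD | Raw limits | Correct limits | Raw ICC |
|---|---|---|---|---|---|---|---|
| 2 | 1.596 | 0.9% | 283.2 | 16.8 | ±33 | ±4 | 0.95 |
| 3 | 2.394 | 1.3% | 421.9 | 20.5 | ±40 | ±6 | 0.92 |

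Without wrapping error the ICC is 1 − 4/5400 or 1 − 9/5400, above 0.99 in both rows. At SD 3, if axes near 0/180 are half or twice as common as uniform, the raw limits are about ±29 or ±57. In the 66-eye repeatability subset the chance of at least one wrapped eye is 1 − (1 − w)^66 = 44% or 59%. If 15% of those eyes had no axis (56 left), it is 39% or 53%.

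If axis were also scored linearly in the primary endpoint, agreement would become 0.90 × (1 − w) and power 98% or 97%.

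**3. Zero cylinder on both devices.** The documents give no share; 5, 10 and 15% are assumed (11, 22 and 32 eyes), with 0.90 agreement in the remaining eyes.

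| Rule | 5% | 10% | 15% |
|---|---|---|---|
| All failed: P(X ≥ 183) with n = 205, 194, 184 | 69% | 2% | <0.1% |
| All failed, count random (agreement 0.855, 0.81, 0.765) | 67% | 9% | 0.2% |
| Dropped (need 174/205, 165/194, 157/184) | 99% | 99% | 98% |
| Sphere and cylinder only, 0.90 to 0.95 success | >99% | >99% | >99% |

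**4. Zero cylinder on one device only.** Suppose 11 to 22 eyes are zero on both devices and succeed at 0.95 on sphere and cylinder. Failing 5 one-device-only eyes gives 96 to 97% power; failing 11 gives 73 to 78%. Scoring them on sphere and cylinder at 0.95 gives above 99%.

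**5. The lenient direction.** Sphere-and-cylinder scoring makes success easier. With true agreement of 0.80 in eyes with an axis and 0.95 in zero-cylinder eyes, overall agreement is 0.815, 0.83 or 0.845 at shares of 10, 20 and 30%. The chance of meeting the goal is then 12.8, 28.4 or 51.0%, against 4.6% at exactly 0.80.

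**6. Per-protocol set, if a blank axis counts as missing.** By eyes, the loss is 5, 10 or 15% of eyes. By patients, it is the same percentages if both eyes always go together, rising to 1 − (1 − s)² = 10, 19 or 28% if eyes are independent (s = share).

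**The case against.** - **Silence is not an instruction.** The plan does not say that axis enters the MI model untransformed or that an angle must be subtracted linearly. A careful analyst would wrap, and a difference of 174 degrees would stand out on the planned plot. This stands in part. But Section 7.7.4 calls axis continuous, linear arithmetic is the plain meaning of the methods named, and a correction chosen after seeing the plot is no longer pre-specified.
- **The wrap problem decides nothing.** No success rule uses the limits or the ICC, and the error works against the device. This stands. A reader might infer that wrap-around threatens the primary test. The documents do not support that: a limit of 10 degrees is naturally read as the smallest angle.
- **The low powers are a construction.** They need an undocumented share of zero-cylinder eyes, every such eye failed, and 0.90 applied only to the others, whereas Section 7.5 sets 0.90 overall. This stands. A reader might infer that the 99% power is wrong or that the plan orders these eyes failed. Neither follows: the 99% reproduces, and the text also allows other readings.
- **Per-protocol losses up to 28% of patients.** A reader might take these from Section 7.2.3, but the synopsis and Section 7.7.3 work by eyes, and Section 7.2.3 makes the analysis optional.
- **Scoring one-device-only eyes on sphere and cylinder is lenient.** This stands. A cylinder of 0.50 D against none passes, while 0.50 D on both devices with axes 12 degrees apart fails, although the vector discrepancy is larger in the first case (0.50/2 = 0.25 against 0.50 × sin 12° = 0.10).
- **Some astigmatism might be required for entry**, because the criterion is worded as a history. The upper-limit-only wording and the intended-use statement rule this out.

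**Conclusion.** Both gaps are real and should be fixed; neither invalidates the design. The wrap-around gap would badly distort the axis limits of agreement, axis ICC and site or subgroup comparisons if the methods were applied as written, even with only about 1% of eyes affected. Its effect in the MI model has not been quantified and may be small in a single-visit study. Those sizes rest on the assumed axis distribution and difference SD.

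The zero-cylinder gap matters more, because the choice of rule can move the primary result. The span from below 0.1% to above 99% power is the range across rules and assumed shares, with the low end a worst case. Dropping these eyes or scoring them on sphere and cylinder leaves 98% or more. All powers treat eyes as independent, as the plan does. The eye-level and patient-level descriptions of the per-protocol set conflict and need reconciling.

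**What to change.** 1. Define the axis difference as the signed difference wrapped to −90 to +90 degrees. Use its absolute value, min(|d|, 180 − |d|), for the primary criterion. Use the signed value for Bland-Altman (plotted against the circular mid-axis) and for site and subgroup comparisons.
2. In the MI model and ICC, replace raw axis A (with cylinder C) by J0 = −(C/2)cos 2A and J45 = −(C/2)sin 2A. Both are zero, not missing, when cylinder is zero. They mix cylinder power with axis, so report the wrapped axis difference alongside.
3. Do not impute an axis for an eye observed to have zero cylinder, and do not count its blank axis as missing data. State whether the per-protocol set is built by eye or by patient.
4. Before data review, state that eyes with zero cylinder on both devices are scored on sphere and cylinder. Fix one rule for eyes with zero cylinder on one device only, and report the primary result under both the sphere-and-cylinder and the failure scoring of those eyes.
5. Because sphere-and-cylinder scoring makes success easier, also report the success proportion and its exact lower bound against 0.80 in eyes with an axis on both devices.

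The cost is SAP wording, variables derived from data already recorded, and a little more analysis. The supplementary result uses fewer eyes (205, 194 or 184 at the assumed shares), with 98 to 99% power at 0.90.

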# 7.7.2 Poolability and Homogeneity of Treatment Effects

Homogeneity of treatment effects across sites will be evaluated by comparing differences between the LFR-260 and the gold standard separately for sphere, cylinder, and axis and also for the vector analysis of sphere and cylinder.

Similarly, differences between measurements from the investigational device and the gold standard device will be summarized by gender, age category, race, and ethnicity to investigate consistency or heterogeneity of the treatment effect across those subgroups, separately for sphere, cylinder, and axis and also for the vector analysis of sphere and cylinder.

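### Section 7.7.1 does not separate right from left eyes, so an axis offset that mirrors between the eyes would be reported as scatter rather than as bias

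*Combined protocol and SAP*

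**What the plan says.** The synopsis (Statistical Considerations) states "The unit of analysis will be the individual eye" and "For each measurement, the paired difference will be computed". Section 4.4 states "Both eyes will be tested, always starting with the right eye", and section 3.2 gives "a total of up to 108 subjects (216 eyes) will be enrolled in the study".

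Section 7.7.1 examines the paired differences "for the three dimensions (sphere, cylinder, and axis) using Bland-Altman agreement analysis". On the outputs it says "This will include determination of the standard deviation of paired differences, the 95% limits of agreement, and an evaluation of systematic bias". It also plans a plot of difference against mean and adds "The relationship between bias and the mean of measurements will characterized".

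Section 7.7.2 compares sites using "differences between the LFR-260 and the gold standard separately for sphere, cylinder, and axis", and summarises the differences by gender, age, race and ethnicity.

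No section splits results by right and left eye, reverses the sign of left-eye axis differences, or says how axis differences are taken across the 0/180 boundary. The documents do not use the words signed or pooled. Both are inferences: a bias cannot be estimated without sign, and an eye-level analysis with no split by side puts both eyes in one set.

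**The concern.** The two eyes are mirror images. I assume that axis is recorded on the same 0-to-180 scale in both eyes; the documents do not say otherwise. A rotation of the LFR-260 axis relative to the phoropter that is outward in both eyes then raises the recorded axis in one eye and lowers it in the other. Averaged over equal numbers of right and left eyes, the two halves cancel.

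The part of section 7.7.1 meant to find systematic bias would then be blind to one kind of systematic error in one of its three components. A constant offset in each eye would be described as imprecision. If the device did worse than hoped on axis, the sponsor would want to tell these two explanations apart. The site and demographic breakdowns in section 7.7.2 do not help, because every such group also mixes right and left eyes.

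**Working it through.** **Plan's own figure.** The plan states no figure for the Bland-Altman analysis. Its only computed figure is the 99% power in section 7.5. It reproduces: with 216 eyes treated as independent and a goal of 0.80, the exact test needs 183 successes (alpha 0.0461) and has power 0.9946 at a true rate of 0.90. This point does not depend on it.

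**Inputs.** From the documents: up to 108 subjects and 216 eyes, hence at most 108 right and 108 left eyes. Assumed, because the documents give neither: mirrored offset m of 2 to 5 degrees, and within-eye SD s of 3 to 5 degrees.

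**Formulas.** Let right-eye differences have mean +m and left-eye differences mean -m, each with SD s and 108 eyes.

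- Pooled bias = (108 × m - 108 × m) / 216 = 0, for any m.
- Pooled SD = √(s² + m² × 216/215).
- Pooled 95% limits = ±1.96 × pooled SD.
- By-eye bias = +m and -m, with SE = s/√108; right-eye limits = m ± 1.96 × s.

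**Main example, m = 3 and s = 3.**

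- Pooled SD = √(9 + 9 × 216/215) = 4.25, and limits = ±1.96 × 4.25 = ±8.3.
- By-eye SE = 3/√108 = 0.29, so the bias is 3/0.2887 = 10.4 standard errors from zero.
- Right-eye limits = 3 ± 5.88, or -2.9 to 8.9; the left-eye limits are the mirror image.

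**Range (degrees).**

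| m | s | Pooled bias | Pooled SD | Pooled limits | By-eye bias | SE per eye | Bias / SE |
|---|---|---|---|---|---|---|---|
| 0 | 3 | 0 | 3.00 | ±5.9 | 0 | 0.29 | 0 |
| 3 | 3 | 0 | 4.25 | ±8.3 | ±3 | 0.29 | 10.4 |
| 5 | 3 | 0 | 5.84 | ±11.4 | ±5 | 0.29 | 17.3 |
| 2 | 4 | 0 | 4.47 | ±8.8 | ±2 | 0.38 | 5.2 |
| 4 | 4 | 0 | 5.66 | ±11.1 | ±4 | 0.38 | 10.4 |
| 2 | 5 | 0 | 5.39 | ±10.6 | ±2 | 0.48 | 4.2 |

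If only 40 eyes per side had a measurable axis, the main example would still give 3/(3/√40) = 6.3 standard errors by eye.

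**Unequal offsets.** Cancellation is complete only when the offsets are equal and opposite and both sides contribute equally. With offsets of +3 and -2 and equal numbers, the pooled bias is (3 - 2)/2 = 0.5 degrees.

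**Does the difference-against-mean plot catch it?** This was simulated with m = s = 4, 108 subjects, left-eye axes set as mirror images of right-eye axes, and 400 runs per pattern. A run was flagged when the correlation of difference with mean exceeded 0.134 in size, roughly the 5% two-sided cut-off for 216 points.

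- Axes spread evenly, or centred on 90 or 180 degrees: mean correlation about 0, flagged in 11 to 12% of runs.
- Right-eye axes mostly on one side of the meridian: mean correlation -0.32 to -0.63, flagged in 99 to 100% of runs.

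The safeguard therefore depends on the axis pattern of the sample. Where it does react, it shows a trend with axis and does not by itself point to a right-left difference.

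**The case against.** The strongest reply is that the problem is hypothetical and has little weight. No section reports or suggests a mirrored axis error. The device description in section 4.2 gives no reason to expect one. Rotation of the eye itself matters only if it differs between the two devices, since each difference is taken within the same eye. The analysis is a supporting one with no acceptance limit. The offset is not lost either: in the main example the pooled limits of ±8.3 are close to the by-eye extreme of 8.9. All of this stands, and it limits the point to the labelling of the error.

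A reader might infer more than the documents support, in three ways.

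- *That the primary result is compromised.* It is not. Sections 7.3 and 7.4 score each eye against a two-sided axis limit, so opposite signs cannot cancel.
- *That such an offset would by itself take the device below the 0.80 goal.* In the main example 74.4% of eyes fall within 5 degrees, against 90.4% without the offset. But the goal applies to the joint criterion over all eyes, not to the 5-degree group. With 99.0% within 10 degrees in the other group, axis alone falls below 0.80 only if the 5-degree group exceeds (0.990 - 0.80)/(0.990 - 0.744) = 77% of eyes. The documents do not give that share.
- *That testing the right eye first hides drift in the same way.* A shift of d in the left eye alone leaves a pooled bias of d/2, so it is halved and not removed. Drift common to both devices drops out of the paired difference, and section 4.8 randomises device order.

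Finally, a by-eye display is not forbidden by section 7.7.1. It is also not planned.

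**Conclusion.** The point holds as a modest improvement to a supporting analysis. Read naturally, the axis bias estimate in section 7.7.1 has expected value zero under any equal and opposite offset, and about m² is added to the variance. Over the assumed range shown, the same data examined by eye would put the bias 4.2 to 17.3 standard errors from zero.

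The conclusion rests on four things: that differences are signed and eyes pooled, which is inferred; a common axis scale for both eyes; near-equal numbers of right and left eyes; and the assumed values of m and s. It does not claim that the LFR-260 has such an offset, only that the planned bias estimate could not identify one. The plot of difference against mean would reveal it for some axis patterns and not for others.

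**What to change.** In section 7.7.1, make two changes for axis.

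1. Take each difference modulo 180 degrees, in the range -90 to +90. Readings of 178 and 2 then differ by 4 degrees in size, not 176. Without this step, either summary below can be distorted.
2. Report bias and 95% limits separately for right and left eyes, or with the sign of left-eye differences reversed, beside the pooled result. If sign reversal is used, keep the pooled result as well, because reversal alone would cancel an offset that has the same sign in both eyes.

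The cost is a sentence or two of SAP wording and one extra table. It needs no added subjects or procedures, provided results are recorded by eye. Each by-eye estimate rests on half the eyes, so it is less precise, but the pooled result remains available. If there is no mirrored offset, the by-eye and pooled results should agree, which is useful evidence for the device.
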